4.1 General Principles

For continuous variables, descriptive summary statistics including number of patients, mean, standard deviation, median, upper and lower quartiles (25th percentile, 75th percentile), and minimum and maximum values will be presented. For categorical variables, counts and percentages will be presented in frequency tables. For continuous variables collected at multiple time points, the descriptive statistics will be provided at each time point. All statistical tests will be conducted using 2-sided tests with 10% Type I error rate unless otherwise stated.

Placebo-treated patients will be pooled and analyzed as a single placebo group. Therefore, four treatment groups will be included and presented in the analysis as 40 mg, 80 mg, 120 mg, and placebo. Patients who are Fesomersen-treated may be pooled and summarized as the pooled treatment group.

The statistical evaluation will be performed by using the software package SAS release 9.2 or higher (SAS Institute Inc., Cary, NC, USA) or if applicable, other software.

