To evaluate the safety of BAY 2976217as compared to placebo	 The incidence of composite of major bleeding and clinically-relevant non-major bleeding during the main and extended treatment periods and within the on-treatment time window, as assessed by blinded CIAC Incidence and severity of TEAEs during the main treatment period and within the on-treatment time window the main and extended treatment periods and within the on-treatment time window the main and extended treatment periods and until 20 weeks after the last study intervention dose
To evaluate the PK and PD of	Pharmacokinetic Endpoints
BAY 2976217	Trough concentrations for 3 dose levels of BAY 2976217
	Maximum change in FXI antigen levels during the main treatment period Maximum change in FXI activity levels during the main treatment period

Overall Design

This is a multicenter, double-blind, randomized, parallel group treatment study with 3 dose cohorts tested against placebo, in ESRD patients who are on HD (including hemodiafiltration) ≥ 3 months, and are receiving hemodialysis for a minimum of 9 hours per week. Participants receiving therapeutic anticoagulation or antiplatelet other than ASA ≤ 150 mg/day are excluded. Approximately 288 participants will be randomized in this study. Participants will be stratified at randomization for use of ASA (yes/no) and CV risk factors (stratum 1 / stratum 2), and will then be randomized to 1 of 3 dose cohorts in a 1:1:1 ratio (Cohort A [40 mg], Cohort B [80 mg], and Cohort C [120 mg]). Within each cohort participants will be randomized to receive either BAY 2976217 or matching placebo (administered at equivalent dose volumes) in a 3:1 ratio. Sponsor, participants and investigators are blinded with respect to active treatment versus matching placebo, but not blinded to dose cohort. With an assumed attrition rate of approximately 15% during the main treatment period, approximately 288 randomized participants would allow for an estimated 240 participants. All standard of care

07 JUL 2021 Page: 13 of 90

hemodialysis therapies as prescribed by their providers, including use of heparins to maintain dialysis circuit patency, will be continued.

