6.1 Study Intervention(s) Administered

Table 6-1: Study interventions administered

Arm Name	BAY 2976217	Placebo
Intervention Name	BAY 2976217	Placebo
Type	Drug	Placebo
Dose Formulation	solution for injection	solution for injection
Unit Dose Strength(s)	100 mg/mL	not applicable
Dosage Level(s)	40 mg, 80 mg or 120 mg (or	• •
3 ()	100 mg if dose reduction is	not applicable
	recommended by DMC)	• •
Route of	SC injection	SC injection
Administration	,	,
Use	Experimental	Placebo
Packaging and	Study intervention will be provided	Study intervention will be provided
Labeling	in 2 mL colorless vials.	in 2 mL colorless vials. Each vial
	Each vial will be labelled as	will be labelled as required per
	required per country requirement.	country requirement.
Current/Former	ION-957943	not applicable
Name(s) or Alias(es)	10.11 00.70 10	пос арриоавіо

DMC = Data Monitoring Committee, SC = Subcutaneous

BAY 2976217 is supplied in 2 mL clear, single-use injection glass vials as a solution. BAY 2976217 is a solution with a concentration of 100 mg/mL. The total content of the glass vial is approximately 1.05 mL, corresponding to 100 mg BAY 2976217. From the total 1.05 mL, 0.8 mL (i.e. 80 mg) are extractable volume and 0.25 mL (i.e. 25 mg) are overfill.

Placebo to BAY 2976217 is supplied in 2 mL clear, single-use glass vials as a solution with a content of 1.05 mL (0.8 ml extractable volume). Further details can be found in the handling instruction provided separately.

Different doses will be achieved by administering a different volume. For dosage regimen and planned duration of intervention see Section 4.1.

Study intervention will be administered any time from 15 minutes before the start of dialysis to 15 mins after the start of dialysis, when administered on a dialysis day.

Study intervention can be administered in the following SC injection areas:

- Abdomen (upper right, upper left, lower right, lower left)
- Thigh
- Outer area of upper arm

Note: Injection is not to be given within two inches (5cm) of any of the following: the umbilicus, the active reaction area of a previous injection, or in areas of the skin that are burned, reddened, inflamed, or swollen. Injections may be administered to a location that previously was involved in an injection site response provided that any symptoms have largely resolved.

07 JUL 2021 Page: 36 of 90

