6.3 Measures to Minimize Bias: Randomization and Blinding

After a participant has signed an ICF, the unique PID will be assigned via IWRS. If a participant is re-screened, a new PID will be assigned. The PID is a 9-digit number consisting of:

Digits 1 to 5 =Unique site number

Digits 6 to 9 = Unique participant number (current participant number within the study site). The unique participant number will start with 7 for each participant.

All participants will be centrally assigned to randomized study intervention using IWRS. Study intervention will be administered at the study visits summarized in SoA (Section 1.3). Before the study is initiated, the log in information and directions for the IWRS will be provided to each site

Participants who meet the entry criteria will be randomized as described in Section 4.1 Participants will be stratified as described in Section 4.1

In order to be able to prepare and administer the correct volume of study intervention to be injected, sponsor, participants and investigators will be aware of dose cohort assignment, but blinded with respect to active treatment versus matching placebo. The CIAC will be blinded to cohort allocation and treatment assignment. DMC will have access to unblinded data as outlined in the DMC charter.

In order to maintain the blind, BAY 2976217 and matching placebo will be packaged in identical vials and each vial will be labeled with a unique, pre-printed number.

The IWRS will be programmed with blind-breaking instructions. In case of an emergency, the investigator has the responsibility for determining if unblinding of a participant's intervention assignment is warranted. If the investigator is unavailable, and a treating physician not associated with the study requests emergency unblinding, the emergency unblinding requests are forwarded to the emergency medical advice 24 hours/7-day service. Participant safety must always be the first consideration in making such a determination. If the investigator decides that unblinding is warranted, the investigator should make every effort to contact the sponsor prior to unblinding a participant's intervention assignment unless this could delay emergency treatment of the participant. If a participant's intervention assignment is

07 JUL 2021 Page: 37 of 90

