$$\left[\frac{IR_{adj} * \chi^2(0.05; 2e)}{2e}; \frac{IR_{adj} * \chi^2(0.95; 2e)}{2e}\right],$$

with $\chi^2(q; 2e)$ the q quantile of a chi square distribution with 2e degrees of freedoms and e the number of participants with an event. (Nelson 1982)

Hazard ratios

With respect to the cause-specific hazards for the respective safety variable, each of the Fesomersen groups will be compared to the placebo group using two-sided log-rank tests. Due to the explorative nature of these analyses, no multiplicity adjustment will be done.

The cause-specific hazard function $h_k(t)$ is the chance that an individual experiences an event of the primary safety outcome in the next instant in time, given that the individual has not had such an event or a competing event up to time t. Cause-specific hazard ratios, cause-specific relative hazard reduction (csRHR; csRHR = $100 \times [1 - \text{cause-specific hazard ratio}]\%$), and corresponding 2-sided 90% and 95% confidence intervals, comparing the hazards for the event-of-interest in each of the Fesomersen groups with the placebo group will be estimated based on three separate cause-specific Cox proportional hazards models as exploratory amalysis. Censoring will be assumed to be independent form the study intervention. For example, for the comparison of the 120 mg Fesomersen group with the placebo group, the corresponding cause-specific Cox proportional hazards model can be described by the following equation:

$$H_k(t,x_i) = h_{0,k}(t) \exp(\beta_k x_i),$$

where

- $h_k(.)$ cause-specific hazard function for primary safety outcome, as a function of time and subject's covariates
- $h_{0,k}(.) \quad \text{unspecified underlying baseline hazard function for primary safety outcome; hazard of an individual with $x_i = 0$ }$
- t time (in days) relative to the date of first administration
- xi treatment group of subject i
 (0 corresponds to "placebo group" and
 1 corresponds to "120mg Fesomersen group")
- β_k unknown parameter (to be estimated); cause-specific hazard ratio = exp(β_k)

k type of event

Probability

As a supportive analysis, the cumulative incidence functions for the respective event-ofinterest will be compared using the Fine and Grays subdistribution hazards model as well as using the Gray's test.

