6.4.3 Sensitivity and Supplementary Safety Analysis

To support the primary study results and to assess the robustness of the analysis, several additional sensitivity and supplementary analyses will be performed.

The primary safety endpoint will be analyzed using the same method described in Section 6.4.1.1 based on SAF analysis set and both TA and OA data scope.

In addition, analysis will be performed with additional bleeding events on SAF analysis set with PA data scope, and SAF analysis set with TA data scope:

- Minor bleeding
 - Minor bleeding will be further categorized as injection site and non-injection site bleeding events.

Additional analysis on the secondary safety endpoints will be performed based on SAF analysis set and TA data scope.

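### Placebo is volume-matched only within each dose cohort but is pooled for analysis, so if local events rise with injection volume, the 40 mg and 120 mg injection-site summaries are biased in opposite directions

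*SAP*

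**What the plan says.** Dose is set by volume. Protocol 6.1 states that "BAY 2976217 is a solution with a concentration of 100 mg/mL" and that "Different doses will be achieved by administering a different volume". Within each cohort, participants receive active drug or "matching placebo (administered at equivalent dose volumes) in a 3:1 ratio" (Protocol 1.1). The cohort is open: "sponsor, participants and investigators will be aware of dose cohort assignment" (Protocol 6.3), although active versus placebo is blinded.

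For analysis, "Placebo-treated patients will be pooled and analyzed as a single placebo group" (SAP 4.1). The four-group presentation is repeated in SAP 3 and 6 and in Protocol 4.1 and 9.4.1.1.

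Local outcomes reach the tables by two routes:
- **Injection-site bleeding.** SAP 6.4.3 plans an analysis of minor bleeding and adds: "Minor bleeding will be further categorized as injection site and non-injection site bleeding events".
- **Injection-site adverse events.** These are defined in Protocol 8.3.9, listed as a safety assessment in Protocol 8.2, and summarised with all TEAEs by system organ class, preferred term and treatment arm (SAP 6.4.2).

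No safety analysis restores the within-cohort matching. SAP 6.4.3.1 repeats the primary safety analysis with the stratification factors, which Protocol 4.1 describes as ASA use and CV risk, not cohort. SAP 6.3.1 separates results by dose cohort, but only for PK.

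**The concern.** The design holds injection volume equal between drug and placebo inside each cohort, and pooling gives that up. Each dose arm is then set against a placebo group whose volume mix differs from its own. For systemic outcomes this hardly matters. For events at the injection site, volume is a plausible cause in its own right, and an open cohort adds a possible difference in how participants report pain or itching.

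At stake is the reading of local tolerability by dose. An inert drug could seem locally worse than placebo at 120 mg and better at 40 mg, and a real local effect at 40 mg could be hidden. Protocol 1.1 gives the parent compound's high injection volumes and its injection site reactions among the reasons for developing this one. Protocol 4.1 says the primary analysis is meant to expedite Phase 3 dose selection.

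**Working it through.** **Inputs.** Concentration 100 mg/mL and, per vial, "0.8 mL (i.e. 80 mg) are extractable volume" (Protocol 6.1). Each cohort has 72 active and 24 placebo participants (Protocol 9.2). Tests, where used, are two-sided at 10% (SAP 4.1). The documents give no injection-site rate by volume, so those risks are assumptions, shown as a range.

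**The plan's own figure.** Protocol Table 9-1 gives ±5.51 points for 5% at n = 60. The check is 1.96 × √(0.05 × 0.95 / 60) = 5.51, which reproduces it. It concerns MB/CRNMB and does not test this point.

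**Volumes.** Dose ÷ 100 mg/mL gives 0.4, 0.8 and 1.2 mL. The last exceeds 0.8 mL, so it needs two vials; the number of injections is not stated. Pooled placebo is 3 × 24 = 72, with mean volume (0.4 + 0.8 + 1.2)/3 = 0.8 mL. Against that mean, 40 mg receives half the volume, 80 mg the same and 120 mg one and a half times.

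**Bias with an inert drug.** Bias = risk at the arm's volume minus the mean risk over the three volumes. For 5/10/15% the mean is 10%, so the bias is -5, 0 and +5 points (risk ratios 0.5, 1.0 and 1.5).

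The table adds results from simulated trials with no drug effect (72 per dose against 72 pooled placebo; 200,000 or more trials per row). The ordering column is the share of trials in which the observed incidences run 40 mg < placebo < 120 mg. The last column is the rejection rate of a two-sided 10% z-test.

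| Assumed risk at 0.4/0.8/1.2 mL | Bias at 40/80/120 mg (points) | Misleading ordering | z-test rejects at 40 mg / 120 mg |
|---|---|---|---|
| 10/10/10% | 0 / 0 / 0 | 12% | 10% / 10% |
| 8/10/12% | -2 / 0 / +2 | 29% | 13% / 13% |
| 2/5/8% | -3 / 0 / +3 | 51% | 29% / 20% |
| 5/10/15% | -5 / 0 / +5 | 63% | 32% / 24% |
| 5/10/20% | -6.7 / -1.7 / +8.3 | 81% | 44% / 40% |

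Against same-cohort placebo (72 v 24) the bias is zero by design, and the z-test rejects in 9% to 12% of trials in every row. A Cochran-Mantel-Haenszel test stratified by cohort stays at about 10%.

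**Price of matching.** At 5/10/15%, the standard error of the 120 mg difference is:
- pooled: √[0.15 × 0.85/72 + 24 × (0.05 × 0.95 + 0.10 × 0.90 + 0.15 × 0.85)/72²] = 5.5 points;
- matched: √[0.15 × 0.85 × (1/72 + 1/24)] = 8.4 points.

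At a 5% risk, the chance of no event among 24 placebo participants is 0.95²⁴ = 29%. SAP 6 calculates log-rank tests and hazard ratios only when each compared arm has an event, so at 40 mg they would often be unavailable.

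**The case against.** The strongest reply is that the driver is assumed. The documents name high injection volume and injection site reactions as separate drawbacks of the parent compound and do not say one caused the other. For this compound, Protocol 1.1 and 4.2 report no evidence of injection site reactions. This stands: with no volume effect there is no bias.

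A reader might infer from the rejection rates that the planned tests have a false-positive rate of 20% to 40%. The documents do not support that. Injection-site TEAEs are only tabulated. The SAP 6.4.1.1 statement that "each of the Fesomersen groups will be compared to the placebo group using two-sided log-rank tests" is written for MB/CRNMB. Carrying it to injection-site bleeding is an inference from SAP 6.4.3, and Protocol 9.1 plans no hypothesis testing.

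A reader might also blame pooling for any dose trend in local events. A gradient across the three active arms mixes dose with volume however placebo is grouped, because dose is given by volume. Placebo shown by cohort does not remove that gradient; it supplies the volume-only gradient to read it against.

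A volume-balanced comparison is already foreseen: SAP 4.1 and 6 allow pooled Fesomersen, and 3:1 allocation in every cohort balances its volume mix against pooled placebo. That stands, but it is discretionary and does not help the by-dose reading. Table layouts sit in a separate specifications document, which might already show placebo by cohort; the SAP does not require it.

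Finally, injection-site events are a subset of the TEAE endpoint, not an endpoint of their own, and neither document names them as a dose-selection criterion. That limits the weight of the point.

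**Conclusion.** The structural point holds. Placebo is matched on volume within cohort, the match is lost by pooling, and no planned safety summary restores it. If local events rise with injection volume, the injection-site bleeding and injection-site TEAE summaries against pooled placebo are too favourable at 40 mg and too unfavourable at 120 mg. In the assumed scenarios with a volume effect, the bias at those two doses runs from 2 to about 8 points; its true size cannot be derived from the documents and may be zero.

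The effect is confined to local events, and mainly to descriptive tables. Formal tests are affected only if the SAP 6.4.1.1 methods are applied to injection-site bleeding. The 80 mg comparison is unbiased under a linear volume effect. Extending the point to the primary endpoint would go too far: there is no reason to expect volume to drive MB/CRNMB, and the CIAC is blinded to cohort and treatment, so pooling is reasonable there. This is a cheap improvement, not a flaw in the main analysis.

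**What to change.** In SAP 4.1, 6.4.2 and 6.4.3, for injection-site bleeding and injection-site TEAEs only:

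1. Show placebo by cohort (about 24 each) beside the pooled column.
2. Present each dose's difference from its own cohort's placebo descriptively, with an exact confidence interval (SAP 6.4.1 already names a method for differences), and without a log-rank test or hazard ratio.
3. Add one Fesomersen v placebo risk difference stratified by cohort (Mantel-Haenszel), using all participants.
4. State that any gradient across the active arms is to be read against the gradient across the placebo cohorts.

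Keep pooled placebo for MB/CRNMB and all other non-local outcomes; no MB/CRNMB-by-cohort table is needed.

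The cost is SAP wording and a few table columns, with no new data or participants. The downside is width: with 24 placebo participants, a 120 mg standard error of 8.4 points means an approximate 95% interval of ±16.5 points (1.96 × 8.4). The within-cohort contrasts therefore show direction and plausibility rather than settle the question, and the stratified estimate carries the overall comparison.

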4.2 Handling of Dropouts

A participant may withdraw from the study at any time at his/her own request or may be withdrawn at any time at the discretion of the investigator for safety, behavioral, compliance, or administrative reasons.

4.2.1 **Permanent Discontinuation of Study Intervention**

A randomized subject who permanently discontinues Fesomersen or placebo before their planned Visit 28 + 5 days window (extended treatment period) or before the last scheduled dose for primary completion, is defined as having had a permanent discontinuation of study intervention (including subjects who were randomized but never started taking any study intervention). The reason for the discontinuation of study intervention will be recorded in the eCRF and source documentation.

The investigator may temporarily discontinue study intervention. If the discontinuation remains necessary > 56 days from the last dose, the participant will be permanently discontinued from study intervention and will enter the post-treatment follow-up period.

The number of subjects who permanently discontinue study intervention and the reason for discontinuation will be displayed by treatment groups. Baseline characteristics will be displayed by permanently discontinue study intervention (yes/no). All data collected until the discontinuation will be presented.

Participants whose discontinuation reason is recorded as COVID-19 will be included and presented here with the reason entered in eCRF.

4.2.2 Lost to Follow Up

A participant will be considered lost to follow-up if he or she repeatedly fails to return for scheduled visits and is unable to be contacted by the study site.

The investigator should make all efforts to determine the survival (vital status) of any participant who would otherwise be lost to follow-up during the treatment period or post-

treatment follow-up period, whether by direct contact or indirect contact with a reliable source (family-member, health-care provider, etc.). A participants survival status will be recorded in the eCRF. If no survival status is known, the contact attempt will be recorded.

4.3 Handling of Missing Data

All missing or partial data will be presented in the subject data listing as they are recorded on the eCRF.

Additional descriptive analyses in the presence of missing data

The number of subjects who prematurely discontinue the study and study intervention for any reason, as well as the reasons for premature discontinuation of study and study intervention, will be reported.

Kaplan-Meier plots for "lost to follow up" will be provided if there are any such incidences.

All dropouts will be carefully evaluated with respect to:

- baseline characteristics,
- potential differences between the treatment groups in the proportion of patient withdrawals or the timing of withdrawals, and
- the reasons for premature discontinuation of study and/or study intervention and potential dropout patterns will be described.

The number, timing, pattern, and reasons for missing values of all relevant efficacy and safety variables will be displayed by means of descriptive statistics and visualized if applicable.

4.4 Interim Analyses and Data Monitoring

No formal interim analysis is planned.

An independent Data Monitoring Committee (DMC) will monitor the safety of the participants. A DMC will frequently review safety data to ensure the safety of the participants in the ongoing study. Further details can be found in the DMC charter.

4.5 Data Rules

4.5.1 Analysis Dates

For the study, the following date and time window are of relevance for the analysis:

• End of Study Date

The end of the study is defined as the date the last participant completes the last protocol-defined visit/contact.

• Primary Completion Date

The primary completion date is the date when the last participant completes the main treatment period . See the below period definitions for data collection in each period.

• Main Treatment Period (actual)

The main treatment period includes a total of 24 weeks

For subjects who *did not* enter the extension period the main treatment period is defined as the period from first dose of study intervention to the last date of dose +28 days.

For subjects who *did* enter the extension period the main treatment period is defined as the period from first dose of study intervention to the administration of study intervention (and hence commencement of the extension period), at visit 22.

• Extended Treatment Period (actual)

The extended treatment period includes a total of up to 24 weeks, from study intervention administration on visit 22 until the date of last dose +28 days or date of last contact (whichever comes first).

• Post-Treatment Follow-up Period (actual)

The post-treatment follow-up period includes a total of 16 weeks. For subjects who *did not* enter the extension period, the follow up is defined as the period from the end of the main treatment period +1 day to the last contact date.

For subjects who *did* enter the extension period, the follow up is defined as the period from the end of extension period + 1 day to the last contact date.

For each subject, the following individual dates are of relevance for analysis:

• Randomization date:

The date of randomization as recorded in the IxRS system.

• Date of the first dose of study intervention:

The date of the first dose of Fesomersen or placebo will be used from the appropriate eCRF page capturing the study intervention.

Date of the earliest logically possible dose of study intervention administration will be used, in cases where the date of the first dose is missing or incomplete.

• Date of the last dose of study intervention:

The date of the last dose of Fesomersen or placebo will be used from the appropriate eCRF page capturing the study intervention.

Date of the latest logically possible dose of study intervention administration will be used, in cases where the date of the last dose is missing or incomplete.

Incomplete dates will be imputed for the analysis as appropriate based on available information.

